12.3. Patient Information and Consent

All parties will ensure protection of patient personal data and will not include patient names or other identifiable data in any reports, publications, or other disclosures, except where required by law.

When study data are compiled for transfer to Pfizer and other authorized parties, patient names, addresses, and other identifiable data will be replaced by a numerical code based on a numbering system provided by Pfizer in order to de-identify study patients. The study site will maintain a confidential list of patients who participated in the study, linking each patient's numerical code to his or her actual identity. In case of data transfer, Pfizer will maintain high standards of confidentiality and protection of patients' personal data consistent with applicable privacy laws.

The informed consent documents must be in compliance with ICH GCP, local regulatory requirements, and legal requirements, including applicable privacy laws.

The informed consent document(s) used during the informed consent process must be reviewed and approved by the sponsor, approved by the IRB/EC before use, and available for inspection.

The investigator must ensure that each study patient, or his or her legally acceptable representative (as allowed by local guideline/practice), is fully informed about the nature and objectives of the study and possible risks associated with participation.

Whenever consent is obtained from patient's legally acceptable representative, the patient's assent (affirmative agreement) must subsequently be obtained when the patient has the capacity to provide assent, as determined by the IRB/EC. If the investigator determines that a patient's decisional capacity is so limited he/she cannot reasonably be consulted, then, as permitted by the IRB/EC and consistent with local regulatory and legal requirements, the patient's assent may be waived with source documentation of the reason assent was not obtained. If the study patient does not provide his or her own consent, the source documents must record why the patient did not provide consent (eg, minor, decisionally-impaired adult), how the investigator determined that the person signing the consent was the patient's legally acceptable representative, the consent signer's relationship to the study patient (eg, parent, spouse), and that the patient's assent was obtained, or waived. If assent is obtained verbally it must be documented in the source documents.

The investigator, or a person designated by the investigator, will obtain written informed consent from each patient or the patient's legally acceptable representative before any

study-specific activity is performed. The investigator will retain the original of each patient's signed consent document.

12.4. Patient Recruitment

Advertisements approved by IRBs/ECs and investigator databases may be used as recruitment procedures.

Pfizer will have an opportunity to review and approve the content of any study recruitment materials directed to potential study patients before such materials are used.

12.5. Reporting of Safety Issues and Serious Breaches of the Protocol or ICH GCP

In the event of any prohibition or restriction imposed (ie, clinical hold) by an applicable competent authority in any area of the world, or if the investigator is aware of any new information that might influence the evaluation of the benefits and risks of the study treatment, Pfizer should be informed immediately.

In addition, the investigator will inform Pfizer immediately of any urgent safety measures taken by the investigator to protect the study patients against any immediate hazard, and of any serious breaches of this protocol or of ICH GCP that the investigator becomes aware of.

13. DEFINITION OF END OF TRIAL

13.1. End of Trial in a Member State

End of trial in a Member State of the European Union (EU) is defined as the time at which it is deemed that a sufficient number of patients have been recruited and completed the study as stated in the regulatory application (ie, clinical trial application [CTA]) and ethics application in the Member State. Poor recruitment (recruiting less than the anticipated number in the CTA) by a Member State is not a reason for premature termination but is considered a normal conclusion to the study in that Member State.

13.2. End of Trial in all other Participating Countries

End of Trial in all other participating countries is defined as Last Patient Last Visit.

14. SPONSOR DISCONTINUATION CRITERIA

Premature termination of this study may occur because of a regulatory authority decision, change in opinion of the IRB/EC, or investigational product safety problems, or at the discretion of Pfizer. In addition, Pfizer retains the right to discontinue development of avelumab at any time.

If a study is prematurely terminated or discontinued, Pfizer will promptly notify the investigator. After notification, the investigator must contact all participating patients and the hospital pharmacy (if applicable) within 1 month. As directed by Pfizer, all study materials must be collected and all CRFs completed to the greatest extent possible.

15. PUBLICATION OF STUDY RESULTS

15.1. Communication of Results by Pfizer

Pfizer fulfills its commitment to publicly disclose clinical trial results through posting the results of studies on www.clinicaltrials.gov (ClinicalTrials.gov), the European Clinical Trials Database (EudraCT), and or www.pfizer.com, and other public registers in accordance with applicable local laws/regulations.

In all cases, study results are reported by Pfizer in an objective, accurate, balanced, and complete manner and are reported regardless of the outcome of the study or the country in which the study was conducted.

www.clinicaltrials.gov

Pfizer posts clinical trial US Basic Results on www.clinicaltrials.gov for Pfizer-sponsored interventional studies conducted in patients that evaluate the safety and/or efficacy of a Pfizer product, regardless of the geographical location in which the study is conducted. US Basic Results are submitted for posting within 1 year of the primary completion date for studies in adult populations or within 6 months of the primary completion date for studies in pediatric populations.

Primary completion date is defined as the date that the final patient was examined or received an intervention for the purposes of final collection of data for the primary outcome, whether the clinical study concluded according to the prespecified protocol or was terminated.

[EudraCT](http://www.eudra.europa.eu)

Pfizer posts EU Basic Results on EudraCT for all Pfizer-sponsored interventional studies that are in scope of EU requirements. EU Basic Results are submitted for posting within 1 year after the primary completion date for studies in adult populations or within 6 months after the primary completion date for studies in pediatric populations.

www.pfizer.com

Pfizer posts Public Disclosure Synopses (clinical study report synopses in which any data that could be used to identify individual patients has been removed) on www.pfizer.com for Pfizer-sponsored interventional studies at the same time the US Basic Results document is posted to www.clinicaltrials.gov.

15.2. Publications by Investigators

Pfizer supports the exercise of academic freedom and has no objection to publication by principal investigator of the results of the study based on information collected or generated by principal investigator, whether or not the results are favorable to the Pfizer product. However, to ensure against inadvertent disclosure of confidential information or unprotected inventions, the investigator will provide Pfizer an opportunity to review any proposed publication or other type of disclosure of the results of the study (collectively, "Publication") before it is submitted or otherwise disclosed.

The investigator will provide any publication to Pfizer at least 30 days before they are submitted for publication or otherwise disclosed. If any patent action is required to protect intellectual property rights, the investigator agrees to delay the disclosure for a period not to exceed an additional 60 days.

The investigator will, on request, remove any previously undisclosed confidential information before disclosure, except for any study- or Pfizer product-related information necessary to the appropriate scientific presentation or understanding of the study results.

If the study is part of a multicenter study, the investigator agrees that the first publication is to be a joint publication covering all study sites, and that any subsequent publications by the principal investigator will reference that primary publication. However, if a joint manuscript has not been submitted for publication within 12 months of completion or termination of the study at all participating sites, the investigator is free to publish separately, subject to the other requirements of this section.

For all publications relating to the study, Institution will comply with recognized ethical standards concerning publications and authorship, including Section II - "Ethical Considerations in the Conduct and Reporting of Research" of the Uniform Requirements for Manuscripts Submitted to Biomedical Journals, <http://www.icmje.org/index.html#authorship>, established by the International Committee of Medical Journal Editors.

Publication of study results is also provided for in the CSA between Pfizer and the institution. In this section entitled [Publications by Investigators](#), the defined terms shall have the meanings given to them in the CSA.

If there is any conflict between the CSA and any Attachments to it, the terms of the CSA control. If there is any conflict between this protocol and the CSA, this protocol will control as to any issue regarding treatment of study patients, and the CSA will control as to all other issues.

Appendix 1. ECOG Performance Status

| Score | Definition |
|-------|---|
| 0 | Fully active, able to carry on all pre-disease activities without restriction |
| 1 | Restricted in physically strenuous activity but ambulatory and able to carry out work of a light or sedentary nature, eg, light house work or office work |
| 2 | Ambulatory and capable of all selfcare but unable to carry out any work activities. Up and about more than 50% of waking hours |
| 3 | Capable of only limited selfcare, confined to bed or chair more than 50% of waking hours |
| 4 | Completely disabled. Cannot carry on any selfcare. Totally confined to bed or chair |
| 5 | Dead |

Appendix 2. Response Evaluation Criteria in Solid Tumors Version 1.1

Adapted from E.A. Eisenhauer, et al. New response evaluation criteria in solid tumours: Revised RECIST guideline (version 1.1). European Journal of Cancer 45 (2009) 228–247.

CATEGORIZING LESIONS AT BASELINE

Measurable Lesions

- Lesions that can be accurately measured in at least one dimension.
- Lesions with longest diameter twice the slice thickness and at least 10 mm or greater when assessed by CT or MRI (slice thickness 5-8 mm).
- Lesions with longest diameter at least 20 mm when assessed by Chest X-ray.
- Superficial lesions with longest diameter 10 mm or greater when assessed by caliper.
- Malignant lymph nodes with the short axis 15 mm or greater when assessed by CT.

NOTE: The short axis is used as the diameter for malignant lymph nodes, longest axis for all other measurable lesions.

Non-measurable disease

Non-measurable disease includes lesions too small to be considered measurable (including nodes with short axis between 10 and 14.9 mm) and truly non-measurable disease such as pleural or pericardial effusions, ascites, inflammatory breast disease, leptomeningeal disease, lymphangitic involvement of skin or lung, clinical lesions that cannot be accurately measured with calipers, abdominal masses identified by physical exam that are not measurable by reproducible imaging techniques.

- Bone disease: Bone disease is non-measurable with the exception of soft tissue components that can be evaluated by CT or MRI and meet the definition of measurability at baseline.
- Previous local treatment: A previously irradiated lesion (or lesion subjected to other local treatment) is non-measurable unless it has progressed since completion of treatment.

Normal sites

- Cystic lesions: Simple cysts should not be considered as malignant lesions and should not be recorded either as target or non-target disease. Cystic lesions thought to represent cystic metastases can be measurable lesions, if they meet the specific definition above. If non-cystic lesions are also present, these are preferred as target lesions.

- Normal nodes: Nodes with short axis <10 mm are considered normal and should not be recorded or followed either as measurable or non-measurable disease.

RECORDING TUMOR ASSESSMENTS

All sites of disease must be assessed at baseline. Baseline assessments should be done as close as possible prior to study start. For an adequate baseline assessment, all required scans must be done within 28 days prior to randomization and all disease must be documented appropriately. If baseline assessment is inadequate, subsequent statuses generally should be indeterminate.

Target lesions

All measurable lesions up to a maximum of 2 lesions per organ, 5 lesions in total, representative of all involved organs, should be identified as target lesions at baseline. Target lesions should be selected on the basis of size (longest lesions) and suitability for accurate repeated measurements. Record the longest diameter for each lesion, except in the case of pathological lymph nodes for which the short axis should be recorded. The sum of the diameters (longest for non-nodal lesions, short axis for nodal lesions) for all target lesions at baseline will be the basis for comparison to assessments performed on study.

If two target lesions coalesce the measurement of the coalesced mass is used. If a large target lesion splits, the sum of the parts is used.

Measurements for target lesions that become small should continue to be recorded. If a target lesion becomes too small to measure, 0 mm should be recorded if the lesion is considered to have disappeared; otherwise a default value of 5 mm should be recorded.

NOTE: When nodal lesions decrease to <10 mm (normal), the actual measurement should still be recorded.

Non-target disease

All non-measurable disease is non-target. All measurable lesions not identified as target lesions are also included as non-target disease. Measurements are not required but rather assessments will be expressed as ABSENT, INDETERMINATE, PRESENT/NOT INCREASED, INCREASED. Multiple non-target lesions in one organ may be recorded as a single item on the case report form (eg, 'multiple enlarged pelvic lymph nodes' or 'multiple liver metastases').

OBJECTIVE RESPONSE STATUS AT EACH EVALUATION

Disease sites must be assessed using the same technique as baseline, including consistent administration of contrast and timing of scanning. If a change needs to be made the case must be discussed with the radiologist to determine if substitution is possible. If not, subsequent objective statuses are indeterminate.

Target disease

- Complete Response (CR): Complete disappearance of all target lesions with the exception of nodal disease. All target nodes must decrease to normal size (short axis <10 mm). All target lesions must be assessed.
- Partial Response (PR): Greater than or equal to 30% decrease under baseline of the sum of diameters of all target measurable lesions. The short diameter is used in the sum for target nodes, while the longest diameter is used in the sum for all other target lesions. All target lesions must be assessed.
- Stable: Does not qualify for CR, PR or Progression. All target lesions must be assessed. Stable can follow PR only in the rare case that the sum increases by less than 20% from the nadir, but enough that a previously documented 30% decrease no longer holds.
- Objective Progression (PD): 20% increase in the sum of diameters of target measurable lesions above the smallest sum observed (over baseline if no decrease in the sum is observed during therapy), with a minimum absolute increase of 5 mm.
- Indeterminate. Progression has not been documented, and
 - One or more target measurable lesions have not been assessed;
 - or
 - Assessment methods used were inconsistent with those used at baseline;
 - or
 - One or more target lesions cannot be measured accurately (eg, poorly visible unless due to being too small to measure);
 - or
 - One or more target lesions were excised or irradiated and have not reappeared or increased.

Non-target disease

- CR: Disappearance of all non-target lesions and normalization of tumor marker levels. All lymph nodes must be 'normal' in size (<10 mm short axis).
- Non-CR/Non-PD: Persistence of any non-target lesions and/or tumor marker level above the normal limits.
- PD: Unequivocal progression of pre-existing lesions. Generally the overall tumor burden must increase sufficiently to merit discontinuation of therapy. In the presence

of SD or PR in target disease, progression due to unequivocal increase in non-target disease should be rare.

- Indeterminate: Progression has not been determined and one or more non-target sites were not assessed or assessment methods were inconsistent with those used at baseline.

New Lesions

The appearance of any new unequivocal malignant lesion indicates PD. If a new lesion is equivocal, for example due to its small size, continued assessment will clarify the etiology. If repeat assessments confirm the lesion, then progression should be recorded on the date of the initial assessment. A lesion identified in an area not previously scanned will be considered a new lesion.

Supplemental Investigations

If CR determination depends on a residual lesion that decreased in size but did not disappear completely, it is recommended the residual lesion be investigated with biopsy or fine needle aspirate. If no disease is identified, objective status is CR.

If progression determination depends on a lesion with an increase possibly due to necrosis, the lesion may be investigated with biopsy or fine needle aspirate to clarify status.

Objective/Subjective Progression

Patients requiring discontinuation of treatment without objective evidence of disease progression should not be reported as PD on tumor assessment CRFs. This should be indicated on the end of treatment CRF as off treatment due to Global Deterioration of Health Status. Every effort should be made to document objective progression even after discontinuation of treatment.

Table 9. Objective Response Status at each Evaluation

| Target Lesions | Non-target Disease | New Lesions | Objective status |
|-----------------------------|---|-------------|------------------|
| CR | CR | No | CR |
| CR | Non-CR/Non-PD | No | PR |
| CR | Indeterminate or Missing | No | PR |
| PR | Non-CR/Non-PD, Indeterminate, or Missing | No | PR |
| SD | Non-CR/Non-PD, Indeterminate, or Missing | No | Stable |
| Indeterminate or Missing | Non-PD | No | Indeterminate |
| PD | Any | Yes or No | PD |
| Any | PD | Yes or No | PD |
| Any | Any | Yes | PD |

If the protocol allows enrollment of patients with only non-target disease, the following table will be used:

Table 10. Objective Response Status at each Evaluation for Patients with Non Target Disease Only

| Non-target Disease | New Lesions | Objective status |
|-------------------------|-------------|------------------|
| CR | No | CR |
| Non-CR/Non-PD | No | Non-CR/Non-PD |
| Indeterminate | No | Indeterminate |
| Unequivocal progression | Yes or No | PD |
| Any | Yes | PD |

Determination of Best Overall Response

The best overall response is the best response recorded from the start of the treatment until disease progression/recurrence (taking as reference for progressive disease the smallest sum on study). For CR and PR, the patient's best response assignment will depend on the achievement of both measurement and confirmation criteria. CR and PR must be confirmed by 2 measurements at least 4 weeks apart. In the case of SD, follow up measurements must have met the SD criteria at least once after study entry at a minimum interval of 6 weeks.

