9.3.2. Analysis of Secondary Endpoints

All analyses will be performed using the Full Analysis Set separately for each co-primary population. The analysis of PFS using the Full Analysis Set described in [Section 9.2.1](#) based on BICR assessment will be repeated based on the investigator's assessment.

The analyses of other tumor-related endpoints will be based on the investigator's assessment, as well as on the BICR.

Progression-Free Survival

PFS is defined as the time from randomization to the date of the first documentation of objective progression of disease (PD) or death due to any cause, whichever occurs first.

PFS data will be censored on the date of the last adequate tumor assessment for patients who do not have an event (PD or death), for patients who start new anti-cancer treatment prior to an event, or for patients with an event after two or more missing tumor assessments. Patients who do not have a baseline tumor assessment or who do not have any post-baseline tumor assessments will be censored on the day of randomization, with a duration of 1 day, unless death occurred on or before the time of the second planned tumor assessment in which case the death will be considered an event.

Within each co-primary population PFS time will be summarized by treatment arm using the Kaplan-Meier method and displayed graphically where appropriate. Confidence intervals (CIs) for the 25th, 50th, and 75th percentiles of the event-free time will be reported. The Cox proportional hazards model will be fitted to compute the treatment hazard ratios and the corresponding 95% CI.

Objective Response (OR)

Objective response is defined as a CR or PR according to RECIST v1.1 ([Appendix 2](#)) recorded from randomization until disease progression or death due to any cause. Both CR and PR must be confirmed by repeat assessments performed no less than 4 weeks after the criteria for response are first met. A patient will be considered to have achieved an OR if the patient has a sustained CR or PR according to RECIST v1.1 definitions. Otherwise, the patient will be considered as a non-responder in the ORR analysis. Additionally, patients with inadequate data for tumor assessment (eg, no baseline assessment or no follow-up assessments) will be considered as non-responders in the ORR analysis.

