5.2.10. Adequate baseline tumor assessment

Adequate baseline is defined using the following criteria:

- All baseline assessments must be within 28 days prior to and including the date of randomization.
- For patients with evidence of disease at baseline, all documented lesions must have non-missing assessments (ie, non-missing measurements for target lesions and non-missing lesions assessment status at baseline for non-target lesions).

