6.2.2.1. Progression Free Survival

Progression-Free Survival (PFS) is defined as the time from the date of randomization to the date of the first documentation of PD or death due to any cause, whichever occurs first.

PFS data will be censored on the date of the last adequate tumor assessment for patients who do not have an event (PD or death), for patients who start a new anti-cancer therapy prior to an event (see Section 5.2.6) or for patients with an event after 2 or more missing tumor assessments. Patients who do not have an adequate baseline tumor assessment or who do not have an adequate post-baseline tumor assessment will be censored on the date of randomization unless death occurred on or before the time of the second planned tumor assessment (ie ≤ 16 weeks after the date of randomization) in which case the death will be considered an event.

In this study antitumor activity will be assessed through radiological tumor assessments conducted at screening, at 8 weeks after randomization, then every 8 (± 3 days) weeks for up to 1 year from randomization, and every 12 weeks (± 3 days) thereafter until PD as assessed by BICR regardless of initiation of subsequent anti-cancer therapy.

The censoring and event date options to be considered for the PFS and DR analysis are presented in Table 8.

$$\text{PFS (months)} = [\text{date of event or censoring} - \text{date of randomization} + 1] / 30.4375$$

Table 8. Outcome and event dates for PFS analyses

Scenario	Date of event/censoring	Outcome
No adequate baseline assessment	Date of randomization ^a	Censored ^a
PD or death - After at most one missing or inadequate post-baseline tumor assessment, OR - ≤ 16 weeks after the date of randomization	Date of PD or death	Event
PD or death - After 2 or more missing or inadequate post-baseline tumor assessments	Date of last adequate tumor assessment ^b documenting no PD before new anti-cancer therapy is given or missed tumor assessments	Censored
No PD and no death	Date of last adequate tumor assessment ^b documenting no PD before new anti-cancer therapy is given or missed tumor assessments	Censored
Treatment discontinuation due to 'Disease progression' without documented progression	Not applicable	Information is ignored. Outcome is derived based on documented progression only.
New anti-cancer therapy given	Date of last adequate tumor assessment ^b documenting no PD before new anti-cancer therapy is given or missed tumor assessments	Censored

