^a However if the patient dies ≤ 16 weeks after the date of randomization the death is an event with date on death date

^b If there are no adequate post-baseline assessments prior to PD or death, then the time without adequate

Scenario	Date of event/censoring	Outcome
assessment should be measured from the date of randomization; if the criteria were met the censoring will be on the date of randomization.		

A stratified log-rank test (1-sided) will be used to compare the PFS time based on BICR assessment between the experimental arm and the control arm.

The treatment effect will be estimated using a Cox's Proportional Hazard model stratified by the randomization strata to calculate the hazard ratio. Each stratum will define a separate baseline hazard function (using the 'STRATA' statement in SAS PROC PHREG), ie for the *i*-th stratum the hazard function is expressed as: $h(i;t) = h(i,0;t) \exp(x\beta)$, where $h(i,0;t)$ defines the baseline hazard function for the *i*-th stratum and x defines the treatment arm (0=control arm, 1= experimental arm) and β is the unknown regression parameter.

Ties will be handled by replacing the proportional hazards model by the discrete logistic model (Ties=Discrete option in SAS PROC PHREG).

Kaplan-Meier estimates (product-limit estimates) will be presented by treatment arm together with a summary of associated statistics including the median PFS time with 2-sided 95% CIs. In particular, the PFS rates at 3, 6, 9, 12 and 15 months will be estimated with corresponding 2-sided 95% CIs. The CIs for the median will be calculated according to Brookmeyer and Crowley (1982) and the CIs for the survival function estimates at the time points defined above will be derived using the log-log transformation according to Kalbfleisch and Prentice (2002) (conftype=loglog default option in SAS Proc LIFETEST) with back transformation to a CI on the untransformed scale. The estimate of the standard error will be computed using Greenwood's formula.

Frequency (number and percentage) of patients with each event type (PD or death) and censoring reasons will be presented by treatment arm. Reasons for censoring will be summarized according to the categories in Table 9 following the hierarchy shown.

Table 9. PFS Censoring Reasons and Hierarchy

Hierarchy	Condition	Censoring Reason
1	No adequate baseline assessment	No adequate baseline assessment
2	Start of new anti-cancer therapy	Start of new anti-cancer therapy

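### The SAP censors PFS at randomization for any inadequate baseline, even one out-of-window scan, so documented progression and later deaths are dropped; on baseline grounds Protocol 9.3.2 does this only when no baseline exists

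*Protocol*

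**What the plan says.** **SAP.** Section 5.2.10 defines an adequate baseline by two tests. The first is timing: "All baseline assessments must be within 28 days prior to and including the date of randomization". The second is completeness: no documented lesion may lack its baseline measurement or status. Section 6.2.2.1 applies the definition to PFS: "Patients who do not have an adequate baseline tumor assessment or who do not have an adequate post-baseline tumor assessment will be censored" at randomization. Footnote a of Table 8 gives the only exception: "However if the patient dies ≤ 16 weeks after the date of randomization the death is an event with date on death date". Table 9 puts the lack of an adequate baseline first among the censoring reasons.

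**Protocol 9.3.2.** The corresponding sentence has no adequacy qualifier: "Patients who do not have a baseline tumor assessment or who do not have any post-baseline tumor assessments will be censored" at randomization, with a duration of 1 day. It has the same exception for a death by the second planned assessment.

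**Protocol Appendix 2.** The adequacy test is close to the SAP's: "For an adequate baseline assessment, all required scans must be done within 28 days prior to randomization and all disease must be documented appropriately". The consequence is softer: "If baseline assessment is inadequate, subsequent statuses generally should be indeterminate". The same appendix says "The appearance of any new unequivocal malignant lesion indicates PD". It also treats a lesion found in a previously unscanned area as new.

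**The concern.** PFS is defined in both documents as time to progression or death from any cause, and it is analyzed in the Full Analysis Set. Take a patient whose baseline is complete except that the bone scan was done on day -29, and who is then scanned on schedule. Under the SAP, that patient's later progression does not count, however clear it is. Nor does a death at, say, month 6, although a death needs no baseline scan at all.

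The early-death exception adds a second problem. For these patients, the outcome decides inclusion: a death by week 16 enters as an event, and everyone else leaves the risk set on day 1. That pulls the Kaplan-Meier curve down. At stake are some lost events, a slightly low PFS estimate and slightly wider intervals.

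**Working it through.** **1. How each document treats each kind of patient**

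| Patient | SAP 6.2.2.1, Table 8 | Protocol 9.3.2 and Appendix 2 |
|---|---|---|
| No baseline assessment | Censored at randomization unless death by week 16 | Same |
| No post-baseline assessment | Same | Same |
| Complete baseline, one scan out of window, later progression | Censored at randomization | Outside the 9.3.2 baseline clause; Appendix 2 makes later statuses generally, not always, indeterminate |
| Same baseline, death after week 16 | Censored at randomization | Nothing in the 9.3.2 baseline clause censors it; the two-missed-assessments rule still applies |
| Incomplete baseline (lesion or region not assessed) | Censored at randomization | As in the two rows above, but a lesion called new may be pre-existing |

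The documents part company in the last three rows. A general row of Table 8 counts progression within 16 weeks as an event, but footnote a limits the inadequate-baseline exception to death, and Table 9 ranks that reason first. The SAP is also uneven. Section 5.2.11 accepts a post-baseline assessment at which PD can be determined, and the reasons for a non-evaluable best response in 6.2.2.3 list an absent baseline, not an inadequate one.

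**2. The 16-week figure.** The second planned scan falls at 8 + 8 = 16 weeks, as the SAP states. In months, 16 × 7 / 30.4375 = 3.68.

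**3. Share d who die by week 16.** With exponential OS as in the sample-size section, d = 1 − exp(−ln 2 × 3.68 / median).

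- BSC, median 12 months: 19.1%.
- Avelumab, all patients, median 17.1 months: 13.9%.
- Avelumab, PD-L1-positive, median 18.5 months: 12.9%.

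So about 81% to 87% of patients with an inadequate baseline would be censored on day 1. For a lower value of d, assume every patient progresses first (exponential, median 5.3 months) and then dies at a constant rate chosen so that median OS is 12 months. This gives d = 9.5%. The 5.3 months is the placebo median in the maintenance lapatinib trial cited in Protocol 1.2.3.1; it is not a design assumption of this trial.

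**4. Effect on the 16-week PFS estimate.** Underlying PFS is S = exp(−ln 2 × 3.68 / 5.3) = 0.618. Let f be the share with an inadequate baseline. The risk set after day 1 is (1 − f) + f·d, and (1 − f)·S of it is event-free at week 16, so the estimate is (1 − f)·S / [(1 − f) + f·d].

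For f = 5%:

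- d = 9.5%: 0.95 × 0.618 / (0.95 + 0.05 × 0.095) = 0.615.
- d = 19.1%: 0.95 × 0.618 / (0.95 + 0.05 × 0.191) = 0.612.

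Patients contributing nothing number 668·f·(1 − d). The standard error grows by roughly 1/√[1 − f(1 − d)] − 1. The documents do not give f, so the values below are assumptions.

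| Assumed f | Patients affected | Contributing nothing | Fall in 16-week PFS (points) | Rise in standard error |
|---|---|---|---|---|
| 2% | 13 | 11-12 | 0.1-0.2 | about 1% |
| 5% | 33 | 27-30 | 0.3-0.6 | about 2% |
| 10% | 67 | 54-60 | 0.6-1.3 | 4-5% |

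**5. Between arms.** The baseline is imaged before randomization, so inadequate baselines should be balanced. At f = 5% there would be 16.7 such patients per arm. With the design medians, 16.7 × 0.191 = 3.2 deaths would be kept on BSC and 16.7 × 0.139 = 2.3 on avelumab, a gap of less than one patient.

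**The case against.** The strongest reply is that the SAP only makes a protocol rule operational. Appendix 2 has the same 28-day test and points the same way. Both documents let the SAP modify protocol plans, with an amendment required only for major changes to the primary endpoint, and PFS is secondary. A post-chemotherapy scan within 28 days is also an eligibility requirement, so cases should be few, and Table 9 will show the number by arm. All of this stands. It limits the size of the point, but it does not explain why a softly worded rule on response status should also remove deaths.

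The second reply concerns new lesions. New means new relative to baseline. If a region was never scanned, pre-existing disease there would be called progression; if the scan is old, a lesion that arose before randomization could be dated after it. This also stands, and it rules out one remedy for all inadequate baselines.

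A reader might infer three stronger things. One is that the protocol censors at randomization only when there is no baseline at all. It does not: 9.3.2 also does so when there are no post-baseline assessments, and the early-death exception is the protocol's own. Another is that the SAP made a change it had no authority to make; the modification clauses answer that. The third is that the rule favors an arm or touches the primary result. OS does not use tumor assessments, and baseline imaging precedes randomization.

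**Conclusion.** The point holds as a discrepancy and a small, avoidable loss of information. For a patient with an inadequate but existing baseline, the SAP discards documented progression and any death after week 16, and includes the patient only if death comes early. Neither Protocol 9.3.2 nor the qualified wording of Appendix 2 requires this.

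Even at an assumed 10% of patients, the 16-week PFS estimate moves by at most about 1.3 points and the standard error by about 5%; at 2% both effects are negligible. These figures rest on the assumed f, on exponential PFS and OS, and on a PFS median borrowed from another trial. The avelumab arm's PFS was not modeled separately. BICR and investigator PFS use the same rule, and the sensitivity analyses in SAP 6.2.2.2 are for OS only, so no planned PFS analysis shows what the rule does.

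**What to change.** Reconcile SAP 5.2.10, 6.2.2.1 and Tables 8-9 with Protocol 9.3.2 and Appendix 2 by separating two cases.

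- **Baseline complete but out of window:** record a protocol deviation, and keep progression and death as PFS events under the ordinary missed-assessment rules.
- **Baseline absent, or incomplete because lesions or regions were not assessed:** keep the present censoring in the main analysis.

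Add a PFS sensitivity analysis that also counts documented progression and deaths in the second group, and split the first line of Table 9 so that each case is counted by arm. In Appendix 2, state that documented progression stands when the baseline is complete but out of window.

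The cost is SAP wording, one derivation rule and one extra analysis on data already collected. The downside is that a few progression dates will rest on an older baseline, and a lesion that arose between that scan and randomization could be dated as progression after randomization.
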